11. RESEARCH PROCEDURES

- *Include a detailed description of all procedures to be performed on the research subject and the schedule for each procedure.*
- *Include any screening procedures for eligibility and/or baseline diagnostic tests*
- *Include procedures being performed to monitor subjects for safety or minimize risks*
- *Include information about drug washout periods*
- *If drugs or biologics are being administered provide information on dosing and route of administration*
- *Clearly indicate which procedures are only being conducted for research purposes.*
- *If any specimens will be used for this research, explain whether they are being collected specifically for research purposes.*
- *Describe any source records that will be used to collect data about subjects*
- *Indicate the data to be collected, including long term follow-up*

Consecutive Sessions of tVNS during robotic therapy intervention

Thirty-six patients with chronic, post-stroke upper extremity hemiparesis will be accepted into this study, and randomized to receive either sham or active tVNS treatment coupled with robotic therapy. There will be 2-3 baseline measurement periods prior to treatment. Following the lead-in period, subjects will participate in a training period consisting of approximately 1 hour sessions robotic therapy paired with tVNS 3x/week for 3 weeks, for a total of 9 sessions. Following the training period, subjects will complete clinical and objective measures both immediately at discharge and again a 3-month follow-up visit.

Lead-in Period

- Week 1, Visit 1 (approximately 90 minutes)
 - Baseline clinical outcome measures
 - Instrumental measures with EMG
 - Medical screening
 - Consent
- Week 1, Visits 2-3 (approximately 60 minutes each)
 - Baseline clinical outcome measures
 - Instrumental measures with EMG

Training Period

- Weeks 2-4, Visits 4-12 (approximately 60 minutes)
 - robotic therapy + tVNS

- Device tolerance questionnaires (every session)

Discharge Evaluation

- Week 4, Visit 13 (approximately 60 minutes)
 - Clinical outcome measures
 - Instrumental measures with EMG

Follow-Up Evaluation

- Week 16, Visit 14 (approximately 60 minutes)
 - Clinical outcome measures
 - Instrumental measures with EMG

**Phase II
Schedule**

	Screen 1	Screen 2	Screen 3	taVNS Tx + robotics	DC eval	3 mo FU
	Visit 1	Visit 2	Visit 3	Visit 4-12	Visit 13	Visit 14
Informed Consent	X					
Medical Hx	X					
Demographic Info	X					
Inclusion Criteria	X					
Neurological Exam	X					
Medication check	X					
Outcome Measures	X	X	X		X	X
Instrumental Assessment	X	X	X		X	X
tVNS (sham or real) + robotics				X		

Clinical Outcome Measures

Fugl-Meyer (Primary): The Fugl-Meyer scale is a valid and reliable evaluation instrument used for measuring performance-based impairment in stroke patients [4, 24-25].

Medical Research Council motor power score (MRC): The MCR is a valid and reliable score that measures strength in isolated muscle groups of the involved shoulder and elbow on an ordinal scale (scale range: 0, no muscle contraction; 5, normal strength) [5, 26].

Wolf Motor Function: The Wolf Motor Function Test is a valid and reliable assessment of upper extremity function by asking the patient to complete 15 motor-based tasks and two strength-based tasks [27].

Robotic Therapy

The MIT-MANUS (the planar robot) was developed in the Newman Laboratory of Biomechanics and Human Rehabilitation at the Massachusetts Institute of Technology and provides customized, goal-directed, robot assisted arm therapy. The hallmark of this system is an impedance controller that modulates the way the robot reacts to mechanical perturbation from a patient or clinician and ensures a gentle compliant behavior. The stability of most robot controllers is vulnerable when contacting objects with unknown dynamics. In contrast, dynamic interaction with highly variable and poorly characterized objects (e.g. neurologically impaired patients) will not de-stabilize the impedance controller, as its stability is extremely robust to the uncertainties due to physical contact [28-32]. Impedance control has been the central contribution of [name] engineering research since the early eighties and has been extensively adopted by other robotics researchers concerned with human-machine interaction [29]. At present the MIT-MANUS impedance controller is implemented using coupled nonlinear position and velocity feedback structured to produce a constant isotropic end-point stiffness and damping. High-bandwidth current-controlled amplifiers produce motor output torques directly proportional to commanded input. These facts make the robot a stable device for operation in a clinical context [28, 30-32].

During planar robot therapy, the patient's hand and wrist are held in a rigid support affixed to the robotic arm, and the patient must reach towards points in space that correspond to the positions of the targets on a screen. Throughout each therapy session, the participant completes a series of flexions, extensions, and rotational movements across the elbow and shoulder joints. If a limb is initially paralyzed, the robot will move it passively, but as motor function returns, the robot will require the patient to initiate progressively more voluntary movement. In this way, the robot safely delivers reproducible movement without tiring and can render the level of training intensity required to alter impairment.

Robotic therapy has been established as a safe and effective tool for upper limb motor recovery after stroke, and is presently a recommended intervention by the American Heart Association [1].

Transcutaneous auricular vagus nerve stimulation (tVNS)

Electrical auricular stimulation will be accomplished using either the Roscoe Medical Transcutaneous Electrical Nerve Stimulation (TENS) 7000 device paired

with ear clip electrodes available from Lhasa Ohms or an Auricular Branch Vagus Nerve Stimulation device co-designed by the CBEM team and fabricated by the MIDI Product Development Corporation. The study will only use one device throughout its conduct for all study participants since using multiple devices will create unnecessary variability. If the Auricular Branch Vagus Nerve Stimulation device from the MIDI Product Development Corporation is received prior to the anticipated study start date and passes internal reviews for design, comfort, and performance, the study will use the Auricular Branch Vagus Nerve Stimulation device from the MIDI Product Development Corporation for the entirety of the study for all subjects. If it is not received by the anticipated start date of this study, the study will utilize only the Roscoe TENS 7000 unit for the entirety of the study for all subjects.

Study Procedure:

tVNS will target the left VNS in order to avoid cardiac side effects associated with right VNS stimulation. The tVNS device will be applied to the left ear using a pair of conductive silicone electrodes, with one electrode contacting the back of the ear and the other electrode on a spring loaded arm, contacting the cymba conchae. Patients will wear the tVNS device for the duration of each 1 hour robotic therapy session. During each session, patients will perform approximately 1000 shoulder/elbow flexion and extension movements and will receive stimulation during only the extensor movements, for a total of 300 stimulations per session. The tVNS current will be delivered during each extensor movement in single 500msec bursts with a frequency of 30Hz and a pulse width of 0.3msec. The current intensity will be individually adjusted to a level just below the patient's reported pain threshold, with amplitudes ranging from 0.1-5.0mA in steps of 100 μ A. The FDA guidance for document for powered muscle stimulators (FDA document 2246) specifies a maximum power density at the electrode site of 250 mW/cm². The MIDI fabricated stimulator has a maximum power density of less than 100 mW/cm², which falls well below the guidance limit for thermal burns. A portable, battery-powered oscilloscope will be used to confirm peak current (for the Roscoe device). These stimulation parameters are similar to parameters that have been demonstrated to be safe in several other tVNS clinical trials [8, 23, 34, 41].

To ensure participant tolerance of stimulation, current will be introduced at the lowest 0.1mA intensity and gradually increased to a level at which the patient just begins to report discomfort, or a maximum of 5mA. The device will then be immediately adjusted to an intensity just below the reported discomfort level, and will remain at this intensity for 10 seconds to confirm patient tolerance. This will be considered the maximum tolerated stimulation intensity threshold for the patient, and stimulation bursts during robotic therapy will then be administered at this level. This tolerability dose will be determined prior to every treatment session for all patients, and recorded in the stimulation tolerance monitoring log. Sham tVNS will have a comparable set-up to active tVNS, with 10 seconds of real current ramping to the maximally tolerated current intensity at commencement,

followed by a slow decrease to no current for the duration of the robotic therapy session.

About the devices:

The Auricular Branch Vagus Nerve Stimulation device fabricated by the MIDI Product Development Corporation is designed to deliver low levels of current to the cymba conchae region of the ear using a pair of conductive silicone electrodes. The electrodes are designed to fit over the left ear and are adjustable in both rotation and location, relative to the rest of the housing, in order to accommodate subjects with different ear sizes. The device has a power switch and USB port for charging. The device is controlled using wireless Bluetooth technology via an application run on a PC that allows control over the amplitude of stimulation, onset, and timing parameters, including pulse width, frequency, and burst patterns.

The Roscoe Medical Transcutaneous Electrical Nerve Stimulation (TENS) 7000 device (www.roscoemedical.com) delivers a programmable electrical current, which can be adjusted for varying frequencies. The device may be modified to include an additional switch allowing the investigator to have precise control of the timing of stimulation. The modification will not change the manner in which the stimulation pulses are generated or delivered. The TENS 7000 will be connected to ear using clip electrodes available from Lhasa Ohms (<http://www.lhasaoms.com/Ear-Clip-Electrodes.html>) to transcutaneously stimulate the cymba conchae region of the ear, targeting the auricular branch of the vagus nerve (e.g. Arnold's nerve). This device does not allow for precise amplitude changes, and will thus be adjusted from its lowest setting gradually to a maximum tolerated threshold by individual patient report as described above in the study procedure. To confirm peak current at this level and ensure patient safety, a portable, battery-powered oscilloscope will be used during the initial adjustment of this device for each patient during each session.

Both the Auricular Branch Vagus Nerve Stimulation device fabricated by the MIDI Product Development Corporation and the Roscoe Medical Transcutaneous Electrical Nerve Stimulation (TENS) 7000 device are considered non-significant risk investigational devices. The Roscoe TENS 7000 was classified as a Class II device by the FDA in 2011 and is FDA cleared (K110390) for over-the-counter sale, with an indication to provide symptomatic relief of chronic intractable pain, relief of acute post-surgical pain, and post-traumatic pain. However, since it will be used on this study to provide transcutaneous electrical stimulation to the auricular branch of the vagus nerve, it is being used off-label as an investigational device for this study. For both devices, the non-significant risk determination was made since they are not intended as an implant, are not purported to be for use in supporting or sustaining life, and do not present a potential for serious risk to the health, safety, or welfare of a subject.

Moreover vagus nerve stimulation, which requires invasive implantation of a stimulator directly to the vagus nerve, has been approved by the FDA for the past two decades for the treatment of seizures, and has been demonstrated to be safe, without any related serious adverse events, and of clinical benefit across several clinical trials for the treatment of tinnitus (n=10), chronic depression (n=494), and more recently chronic, post-stroke hemiparesis (n=9) [8, 11, 21]. Transcutaneous electrical auricular stimulation in which the electrical current is delivered more safely and non-invasively via a transcutaneous route at the cymba concha of the ear, is also currently approved in Europe for the treatment of seizures. tVNS has been similarly demonstrated to be safe and without any related serious adverse events across several clinical trials in the treatment of tinnitus (n=24), treatment resistant epilepsy (n=30), and chronic post-stroke hemiparesis (n=7) [23, 34, 41]. Additionally, the tVNS device which we propose to use in this study has been approved by the Northwell IRB in an investigation involving healthy controls (IRB# HS16-0530) and patients with Lupus (IRB# HS16-0171). These investigations have also been conducted without any related serious adverse events.

Electromyography (EMG)

Electrical activity of the muscle will be differentially recorded during tVNS sessions using a bipolar electrode montage placed on the belly of the muscle. Recordings will be made from the biceps and triceps brachii, pectoralis major, rhomboideus, and/or the deltoids, which are some of the important muscles responsible for flexion and extension of the shoulder and elbow.

Randomization

Subjects will be stratified by established clinical impairment levels based upon admission Upper Extremity Fugl Meyer scores (low function <23 & moderate function 23-44) such that there are an equal number of low and high functioning patients in each treatment group. Subjects will then be randomized to either the active or sham tVNS group [28]. Assignment will be predetermined by a randomized assignment list, created prior to the enrollment of the first subject by an investigator from the CBEM team who is not directly involved in subject treatment. There will be concealed allocation of treatment assignment such that investigators involved in subject screening, consent, and clinical scoring will be blinded to treatment condition.

Blinding

This will be a double-blind pilot study in which subjects will be randomly assigned to either the sham or active tVNS conditions. Subjects will be told that they have a 50-50 chance of receiving either active or sham stimulation, but they will not be told which condition they receive. Additionally, the assigned clinical evaluators will remain blinded to condition. For each study session, stimulation condition will be programmed into the device by the RA or members of the CBEM team who are not performing clinical measures.

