12. STATISTICAL ANALYSIS

- *Describe how your data will be used to test the hypotheses.*
- *State clearly what variables will be tested and what statistical tests will be used.*
- *Include sample size calculations.*
- *If this is a pilot study, state which variables will be examined for hypothesis generation in later studies.*

For our primary outcome measure, we will investigate whether tVNS paired in a closed loop with robotic therapy changes peak amplitude EMG activation in muscle groups along the shoulder and elbow. We hypothesize that upper extremity flexor synergy will be significantly improved when active tVNS is applied during extensor movements as compared to a sham condition, and will lead to an increase in EMG peak activation at the triceps brachii (elbow extensor muscle). This will be examined with a 2x3 ANOVA with condition (active stimulation vs. sham) and time (peak amplitude of EMG activation during extensor movements at admission, discharge, and follow-up) as factors.

For our secondary outcome measure, we will test whether active tVNS during extensor movements paired in a closed loop with intensive robotic intervention (9 sessions) significantly improves upper extremity motor function as compared to sham tVNS paired with intensity-matched robotics. This will be examined with a 2x3 Friedman ANOVA with condition (active vs. sham tVNS) and time (upper extremity fugl meyer score at admission, discharge, and 3 month FU) as factors.

Since this is a pilot study, there are presently no data from which we can derive a power calculation. However, we propose to enroll 36 subjects, in order to achieve a target of at least fifteen subjects per treatment group and also allow for a 10-15% drop out rate. In our extensive past experience with upper limb hemiparesis rehabilitation studies, 10-15 subjects per treatment group is required at minimum to capture a measurable treatment response. Additionally, two other early pilot studies investigating post-stroke upper limb motor rehabilitation combined with VNS found a significant improvement in motor performance with nine and fourteen subjects per treatment group (e.g. sham and active VNS), respectively [8 & 41].

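### Randomisation is stratified by admission Fugl-Meyer level, but neither planned analysis uses the stratum, so power is lost if recovery differs between the two levels

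*Combined protocol and SAP*

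**What the plan says.** Section 11, Randomization, sets two strata: "Subjects will be stratified by established clinical impairment levels based upon admission Upper Extremity Fugl Meyer scores (low function <23 & moderate function 23-44". The purpose given for this is balance between the arms: "such that there are an equal number of low and high functioning patients in each treatment group". Patients are then randomised: "Assignment will be predetermined by a randomized assignment list, created prior to the enrollment of the first subject". Under Blinding, the ratio is 1:1: "Subjects will be told that they have a 50-50 chance of receiving either active or sham stimulation".

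Section 12, primary outcome (peak EMG amplitude at admission, discharge and follow-up): "This will be examined with a 2x3 ANOVA with condition (active stimulation vs. sham) and time". Section 12, secondary outcome (Fugl-Meyer at the same three times): "This will be examined with a 2x3 Friedman ANOVA with condition (active vs. sham tVNS) and time".

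No stratum term, baseline covariate or stratified test appears for either outcome. On size: "we propose to enroll 36 subjects, in order to achieve a target of at least fifteen subjects per treatment group", with 10-15% drop-out allowed for. On power: "there are presently no data from which we can derive a power calculation".

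**The concern.** A factor is normally used to stratify because it is expected to predict outcome. Balancing the arms on it makes the treatment difference less variable. An analysis that omits the factor does not see this gain: the stratum variation stays in the residual, the standard error is larger than the true one, and the test rejects less often than its nominal level. A trial that aims for about 15 completers per arm has little precision to give away, and recovering it costs almost nothing.

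**Working it through.** **Inputs from the documents.** 36 enrolled, 1:1, 10-15% drop-out, at least 15 per arm, two strata. The enrolment figure reproduces: 30/(1 - 0.15) = 35.3, rounded up to 36 (at 10%, 30/0.90 = 33.3, rounded up to 34). Expected completers per arm are 36 x 0.90/2 = 16.2 or 36 x 0.85/2 = 15.3.

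**Inputs assumed, because the documents give none.** Two-sided 5% test, effect size, stratum split, and the share of variance in change that the stratum explains (written R²).

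**Step 1: level or change.** Admission is one of the three time levels, so the condition-by-time test works on differences within a patient, and a constant difference in level between strata cancels. A simulated 2x3 mixed ANOVA confirms this (16 per arm, 4,000 replicates per cell, effect 1.0 SD). With strata 3 between-subject SD apart in level and not at all in change, type I error was 4.6% unadjusted and 4.7% adjusted, and power 81.3% and 80.9%. Only stratum differences in change matter.

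**Step 2: size when change differs.** Take change from admission with total SD 1 within arm, n = 16 per arm, balanced within stratum, effect 0.8.

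- True variance of the treatment difference: (2/n)(1 - R²).
- Variance that the unadjusted test uses: about 2/n.
- Effective threshold of the unadjusted test, on the true scale: 2.042/√(1 - R²), where 2.042 is the 97.5% point of t on 30 df.
- Noncentrality: 0.8/√[(2/16)(1 - R²)] = 2.263/√(1 - R²). The adjusted test keeps its threshold at 2.045 (29 df).

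| R² | Effective threshold, unadjusted | Noncentrality | Type I error, unadjusted | Power, unadjusted | Power, adjusted |
|---|---|---|---|---|---|
| 0% | 2.042 | 2.263 | 5.0% | 59% | 59% |
| 10% | 2.153 | 2.385 | 4.0% | 60% | 64% |
| 20% | 2.283 | 2.530 | 3.0% | 60% | 69% |
| 30% | 2.441 | 2.704 | 2.1% | 61% | 74% |

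The formula is approximate. A 20,000-replicate simulation gives type I error 4.9/4.0/2.9/2.1%, unadjusted power 59/60/60/60% and adjusted power 59/64/69/74%.

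**Step 3: a second setting.** 30 completers from 36, strata of 18 and 18, blocks of 4 within stratum, effect 1.0 residual SD, 6,000 simulated trials per scenario. The stratum gap in change, g, is in residual SD. With equal strata, R² = (g/2)²/[1 + (g/2)²], so g = 0.5, 1.0 and 1.5 correspond to 6%, 20% and 36%.

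| g | 0 | 0.5 | 1.0 | 1.5 |
|---|---|---|---|---|
| Type I error, unadjusted | 0.051 | 0.046 | 0.033 | 0.019 |
| Power, unadjusted | 0.75 | 0.73 | 0.66 | 0.56 |
| Power, adjusted | 0.74 | 0.74 | 0.74 | 0.74 |

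Unadjusted power falls here because the effect is scaled to the residual SD. In Step 2 it is scaled to the total SD, so the same loss shows as adjusted power rising.

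**Step 4: what the term must be.** In the 2x3 model, a stratum main effect alone acts on patient averages and leaves the condition-by-time test unchanged. The stratum-by-time term is what removes the variance in change. It takes (2 - 1) x (3 - 1) = 2 df, plus 1 for the main effect.

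**The case against.** The strongest reply is that the damage is conditional and in the safe direction. The condition-by-time test already removes each patient's level, which is what Fugl-Meyer strata most obviously separate. At no stratum effect on change nothing is lost, and at 0.5 SD the loss is about one point (0.73 against about 0.74). The larger losses need a large assumed effect. The trial is a pilot with no stated power target, and omitting the stratum cannot manufacture a positive result. All of this stands. It limits the size of the point without removing it, because adjustment costs almost nothing when the stratum turns out not to matter.

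It is also right that a Friedman test takes no stratum term or covariate, so the Fugl-Meyer analysis needs a different test.

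A reader might go further and infer that the assignment list will fail to deliver the promised balance. An unblocked 1:1 list for 36 patients would leave one arm with 14 or fewer with probability 2 x P(Bin(36, 0.5) ≤ 14) = 0.243. With an assumed 18/18 stratum split, it would give exact equality in both strata with probability [C(18,9)/2^18]² = 0.034. But Section 11 nowhere says that the list is unblocked. It describes stratified allocation aimed at equal numbers, which is compatible with a separate blocked list for each stratum. These figures show what an unblocked list would do. They do not show a failure of this plan.

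**Conclusion.** The point holds in limited form. The plan stratifies on Fugl-Meyer level and omits it from both analyses. If change differs between levels, the condition-by-time comparison loses power, and when the arms are balanced within strata it is also conservative. Under the Step 2 assumptions, the loss is about 4, 9 and 14 points of power at 10, 20 and 30% of the variance in change, and nil at 0%. The calculations compare change between two time points. For the rank-based Fugl-Meyer analysis they indicate direction, not exact size.

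A reader might infer that the planned results would be biased or their type I error inflated. Neither follows: in the unadjusted analyses above, type I error was at or below about 5%. Nor can the loss be read off how far apart the strata start, since level differences alone cost nothing. This is a worthwhile improvement in efficiency and does not threaten validity.

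**What to change.** - **EMG:** add stratum (below 23 against 23-44) and stratum-by-time to the 2x3 model, or model change from admission with stratum as a factor.
- **Fugl-Meyer:** replace the Friedman test with a rank test of change stratified by level, or with a model of change adjusted for stratum or the admission score. Both are not needed, since one is a dichotomy of the other.
- **Clarification only:** state in Section 11 that the assignment list is blocked within each stratum. With blocks of 4 (an assumed size), the arms would differ by at most 2 patients in any stratum.

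The cost is up to three degrees of freedom in the 2x3 model, or one in a change-score model, and a new test for the secondary outcome. The rest is wording, with no change to sample size, visits or data collected. The change should be made before unblinding.

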8. NUMBER OF SUBJECTS

- *Indicate the total number of subjects to be accrued locally. If applicable, distinguish between the number of subjects who are expected to be pre-screened, enrolled (consent obtained), randomized and complete the research procedures.*
- *If your study includes different cohorts, include the total number of subjects in each cohort.*
- *If this is multisite study, include total number of subjects across all sites.*

This is a double-blind, sham-controlled pilot study. The total target enrollment is 36 subjects with post-stroke hemiparesis. Only patients who meet inclusion criteria following screening will be enrolled. We have anticipated a 10-15% drop-out rate in determining target enrollment.

This study will use a randomized controlled study design to determine whether nine repeated treatments of upper extremity robotic therapy paired with tVNS delivered only during extensor movements significantly changes objective EMG activation patterns and significantly improves clinical measures of upper extremity motor function in patients with chronic post-stroke hemiparesis as compared to a sham condition.

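### Staff who set active or sham stimulation are barred only from clinical measures, so the rule lets someone who knows the arm handle the EMG primary outcome

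*Combined protocol and SAP*

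**What the plan says.** Section 11 names the people who are kept blind. Subjects are not told their condition. Under Blinding, "the assigned clinical evaluators will remain blinded to condition". Under Randomization, "investigators involved in subject screening, consent, and clinical scoring will be blinded to treatment condition". For those who set the arm on the device, the only restriction is that "stimulation condition will be programmed into the device by the RA or members of the CBEM team who are not performing clinical measures".

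EMG peak amplitude in the extensor muscles is the primary efficacy measure in Section 10 and the primary outcome in Section 12, where it is analysed at admission, discharge and follow-up. Fugl-Meyer is secondary in both sections. EMG is scheduled at Visits 1-3, 13 and 14. Nothing in the protocol says who records, processes or analyses it, or whether those people know the arm.

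**The concern.** A blinding rule has to cover whoever can influence the primary outcome. This one is written around clinical measures. If that term leaves out EMG, the safeguard covers the secondary outcome and misses the primary one.

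The documents do not describe how EMG is processed. As a general assumption, placing electrodes and encouraging the subject at recording, and selecting trials and rejecting artefact at processing, can involve judgement. Where they do, knowing the arm could shift peak amplitude differently in the two groups. The planned ANOVA could not separate such a shift from a treatment effect.

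**Working it through.** No figure in the plan bears directly on this point, so the check is one of wording and schedule.

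**Step 1. Does the term clinical measures include EMG?**

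| Place | How EMG and clinical measures appear |
|---|---|
| Section 3, earlier work on spinal stimulation | Force transducer and EMG amplitudes are examples of objective measures; Tardieu and MAS are the clinical ones |
| Section 4 | EMG is Aim 1; clinical measures of motor function are Aim 2 |
| Section 8 | The treatment is tested for whether it "significantly changes objective EMG activation patterns and significantly improves clinical measures of upper extremity motor function" |
| Section 11, procedures text | "subjects will complete clinical and objective measures both immediately at discharge and again a 3-month follow-up visit" |
| Section 11, visit list | "Instrumental measures with EMG" is a separate item from the clinical outcome measures |
| Section 11, schedule table | "Instrumental Assessment" is a separate row from the outcome measures |
| Section 11, Clinical Outcome Measures | Fugl-Meyer, MRC motor power and Wolf Motor Function only |

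The usage is consistent. EMG falls outside the term.

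**Step 2. Does another statement cover EMG staff?**

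- The double-blind label (Sections 8 and 11) is general. Where Section 11 spells it out, it names subjects and clinical evaluators.
- The delegation log (Section 5) assigns tasks and sets no blinding condition.
- Storage by subject ID (Section 14) does not hide the arm from someone who programmed that subject's sessions.

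**Step 3. Which EMG data are exposed?**

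- Programming takes place at Visits 4-12, which are 9 sessions.
- EMG at Visits 1-3 comes before programming. Those visits are headed as screening visits, and screening investigators are blinded, so baseline recording is less exposed.
- EMG at Visits 13 and 14 comes after programming.
- The ANOVA uses 3 time points, of which 2 (discharge and follow-up) are recorded after programming begins. Off-line processing of all 3 is open to anyone.

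**Step 4. Points that bear on how wide the gap is.**

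- Grammatically, the restriction may apply only to the CBEM members, which would leave the RA with no bar at all.
- Section 5 describes a Research Assistant skilled in EMG analysis. The abbreviation RA is not defined in Section 11, so identifying the two is an inference, and the conclusion does not depend on it.
- The Electromyography paragraph of Section 11 places recording within the stimulation sessions, whereas the schedule lists EMG only at Visits 1-3, 13 and 14. The count in Step 3 follows the schedule, which is the narrower reading.

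**The case against.** The case for leaving the text alone has several parts.

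- **Silence is not permission.** No sentence assigns EMG to anyone who knows the arm, and the trial is described as double-blind. That is true, and it limits the claim to what the rule allows. But the protocol does state a rule on who must be kept apart, and that rule stops short of the primary outcome.
- **The blinded evaluators may run EMG.** Visits 13 and 14 are single evaluation visits of about 60 minutes that include both clinical measures and EMG, so the same staff may well do both. This is plausible for recording, though not stated. It does not reach processing.
- **EMG is an instrument reading.** This reduces the room for judgement. The documents nevertheless describe no automated or blinded processing, so they do not show that judgement is absent. Equally, they do not show that it is present, and the harm remains an assumption.
- **Fugl-Meyer is tagged as primary in the list of clinical outcomes in Section 11.** If that tag governed, the safeguard would cover the primary outcome. Sections 10 and 12 both name EMG, so the tag does not carry the point, but it needs reconciling.
- **Separating the roles may cost more than it seems.** Section 5 records EMG expertise for one person. If that person is the RA, CBEM members would have to program up to 36 × 9 = 324 sessions. That is a real constraint on staffing. Section 11 already permits CBEM members to program, so it requires no new staff category.

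**Conclusion.** The concern holds. Following Section 11 to the letter, a person who knows the arm may record EMG at discharge and follow-up and may process EMG from every visit, while the Fugl-Meyer score is protected.

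Confidence in this reading of the text is high. It rests on the protocol's own use of the term clinical measures and on EMG being primary, as Sections 10 and 12 state. Whether bias would follow, and how large it would be, cannot be judged from the documents. The count of 2 time points out of 3 describes scope and does not measure bias. The change should be made because it is cheap and protects the primary outcome, even though nothing shows that unblinded handling is planned.

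**What to change.** In Section 11 (Blinding):

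1. Restrict programming to staff who perform neither clinical measures nor EMG acquisition, processing or analysis. Word it so that it plainly binds both the RA and the CBEM members, and define RA.
2. State by role who records and who processes EMG, and that they are blinded to condition.
3. Process EMG files under codes that hide the arm. Hiding the visit as well is optional.
4. Finalise the EMG peak-amplitude dataset before the assignment list is released for analysis.

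In the same revision, reconcile the timing of EMG recording between the Electromyography paragraph and the schedule, and reconcile the Fugl-Meyer primary tag with Sections 10 and 12.

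The cost is two or three sentences for the blinding rule, a file-coding step, and less freedom in assigning staff to programming and EMG. Sample size and significance level are unaffected.
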